## 9.5 Prior and Concomitant Medications

Subjects will abstain from all restricted concomitant medications as described in the exclusion criteria ([Section 8.2](#)).

Information regarding all prior and concomitant medications, including the subject's CF medications, other medications, and herbal and naturopathic remedies administered from

4 weeks before the Screening Period through the Safety Follow-up Visit will be recorded in each subject's source documents and electronic case report form (eCRF).

- It is recommended that subjects remain on their stable medication regimen for CF from 4 weeks before Day 1 through Week 8 or, if applicable, through the Safety Follow-up Visit. Stable medication regimen is defined as the current medication regimen for CF (except for commercially available CFTR modulators) that subjects have been following for at least 4 weeks before Day 1. Subjects must not initiate long-term treatment with new medication from 28 days before Day 1 through the Safety Follow-up Visit unless discussed and approved by the Vertex medical monitor. Guidelines for stable medication regimens for CF are as follows:
  - Subjects who are taking daily inhaled tobramycin or other chronically inhaled antibiotics should remain on that regimen throughout the study.
  - Subjects who are on inhaled cycling antibiotics should continue on their prior schedule. The timing of the first dose of study drug should be synchronized as closely as possible to the first day of inhaled cycling antibiotics in the cycle.
  - Subjects who alternate 2 different antibiotics monthly should remain on the same schedule during the study. The timing of the first dose of study drug should be synchronized as closely as possible to the first day of 1 of the inhaled alternating antibiotics.
- Subjects may receive doses of prednisone (or prednisolone) of up to 10 mg/day (chronically), or prednisone (or prednisolone) 60 mg qd for up to 5 days with tapering down to 10 mg/day within 2 weeks, without prior approval of the medical monitor.
- Information about bronchodilator use during the study will be collected and documented. Subjects who are using a bronchodilator must have their spirometry assessments performed according to the guidelines provided in [Section 11.4.2](#).

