## **11.4 Efficacy**

### **11.4.1 Lung Clearance Index**

LCI derived from N2-MBW testing will be conducted at visits specified in [Table 3-1](#) to evaluate the effect of TEZ/IVA on lung ventilation inhomogeneity. LCI2.5 represents the number of lung turnovers required to reduce the end tidal inert gas concentration to 1/40th of its starting value,

[REDACTED]

Pre-bronchodilator MBW testing is defined as MBW testing performed for subjects who have

- withheld their short-acting bronchodilator (e.g., albuterol) or anticholinergic (e.g., Atrovent®) for more than 4 hours before the MBW testing;

- withheld their long-acting bronchodilator (e.g., salmeterol) more than 12 hours before the MBW testing; and
- withheld their once-daily, long-acting bronchodilator (e.g., tiotropium bromide [Spiriva®]) for more than 24 hours before the MBW testing.

MBW testing should be performed “pre-bronchodilator.” MBW testing must be performed before dosing, unless noted otherwise. In the event that a subject forgets to withhold bronchodilator(s), MBW testing should be performed according to the following:

- If a subject's Day 1 MBW testing is pre-bronchodilator, but on a subsequent visit, the subject forgets to withhold bronchodilator use, post-bronchodilator MBW testing will be obtained for that visit only, and the visit will not be rescheduled.
- If on Day 1, the subject forgets to withhold his/her dose of bronchodilator, MBW testing should be performed post-bronchodilator and all subsequent MBW testing (according to the Schedule of Assessments detailed for LCI in [Table 3-1](#)) should be performed post-bronchodilator.
- Subjects and their parent/caregiver should not be informed of their study-related LCI results during the Treatment Period.

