#### 11.4.2 Spirometry

Spirometry will be performed according to the ATS/ERS Guidelines at the time points noted in [Table 3-1](#) according to the additional guidelines that follow.

Pre-bronchodilator spirometry is defined as spirometry testing performed for subjects who have

- withheld their short-acting bronchodilator (e.g., albuterol) or anticholinergic (e.g., Atrovent) for more than 4 hours before the spirometry assessment;
- withheld their long-acting bronchodilator (e.g., salmeterol) more than 12 hours before the spirometry assessment; and
- withheld their once-daily, long-acting bronchodilator (e.g., tiotropium bromide [Spiriva]) for more than 24 hours before the spirometry assessment.

All spirometry assessments should be performed “pre-bronchodilator.” During the Treatment Period, spirometry assessments must be performed before dosing, unless noted otherwise. In the event that a subject forgets to withhold bronchodilator(s), spirometry should be performed according to the following:

- If a subject's Day 1 spirometry is pre-bronchodilator, but on a subsequent visit, the subject forgets to withhold bronchodilator use, a post-bronchodilator spirometry will be obtained for that visit only, and the visit will not be rescheduled.
- If on Day 1, the subject forgets to withhold his/her dose of bronchodilator, spirometry should be performed post-bronchodilator and all subsequent spirometric measurements (according to the Schedule of Assessments detailed in [Table 3-1](#)) should be performed post-bronchodilator.
- Each spirometry assessment will be recorded in the source documents as pre-bronchodilator or post-bronchodilator.

The parameters listed below will be normalized using the standards of GLI.

- FEV1 (L)
- Forced vital capacity (FVC) (L)
- FEV1/FVC (ratio)
- Forced expiratory flow, midexpiratory phase (FEF25%-75%) (L/s)

All sites will be provided with spirometers and associated materials to be used for all study assessments by the central spirometry service. Spirometry data will be transmitted to a centralized spirometry service for quality review.

Subjects and their parent/caregiver should not be informed of their study-related spirometry results during the Treatment Period.

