7.2 Sample Size and Power

The sample size of this study is driven by demonstrating that the treatment effect of TEZ/IVA excludes a maximum possible placebo effect, which is based on a within-group comparison (change from baseline in LCI_{2.5} in subjects on TEZ/IVA). If the corresponding 2-sided 95% CI of the change from baseline in LCI_{2.5} in subjects on TEZ/IVA excludes the pre-defined maximum possible placebo effect, it will be considered that the study has achieved its primary objective.

A placebo effect is not expected with LCI, because clinical data from other Vertex CFTR modulator studies consistently demonstrated a worsening of lung function (i.e., an increase from baseline in LCI) in the absence of CFTR modulator treatment. Study VX14-809-109 (Study 809-109) evaluated treatment with LUM/IVA in F/F subjects aged 6 through 11 years using change from baseline in LCI as the primary efficacy endpoint and provided the most relevant clinical LCI data available in the younger age group of CF subjects. In Study 809-

109, the placebo group had a mean worsening in LCI_{2.5} of 0.08 units with an SD of 1.41 (higher numbers indicate a worsening of an LCI measurement); the one-sided 90% lower bound was -0.10 and is used as an estimate for the pre-defined maximum possible placebo effect for Study 115.

Accounting for a 10% dropout rate, approximately 40 subjects in the TEZ/IVA group will provide at least 90% power to exclude -0.10 if the true mean change is -0.9 with an SD of 1.41 using a two-sided alpha of 0.05. The current estimate of the maximum possible placebo effect is based on Study 809-109 placebo data in pediatric F/F subjects with CF.

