9.3 Efficacy Analysis

There is no multiplicity adjustment in this study; *P*-values provided for the secondary and other endpoints are considered nominal.

All efficacy analyses described in this section will be based on the FAS, unless otherwise specified. The analysis will include all available measurements through the last scheduled on-treatment visit, including measurements after treatment discontinuation.

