9.3.1 Analysis of the Primary Efficacy Variable

The primary efficacy endpoint is the absolute change in $LCI_{2.5}$ from baseline through Week 8. The objective of the primary efficacy endpoint analysis is to demonstrate that the mean absolute change from baseline in $LCI_{2.5}$ through Week 8 excludes a pre-defined maximum placebo effect in subjects in the TEZ/IVA group.

The primary analysis will be performed using a restricted maximum likelihood (REML)-based mixed-effect model for repeated measures (MMRM) for the subjects in the TEZ/IVA treatment group in the FAS population. The model will include absolute change from baseline in $LCI_{2.5}$ (including all measurements up to Week 8 [inclusive], both on treatment measurements and measurements after treatment discontinuation) as the dependent variable, and visit (as a class variable) as a fixed effect, with adjustment for mutation group based on the second *CFTR* allele (F/F and F/RF) and baseline $LCI_{2.5}$ (continuous) value as covariates, and subject as a random effect. An unconstructed covariance structure will be used to model the within-subject errors. If the model fails to converge, a compound symmetry covariance structure will be considered. The degrees of freedom of the denominator will be approximated by the Kenward-Roger's method².

The primary results obtained from the model will be the estimated average treatment effect through Week 8 in $LCI_{2.5}$ for subjects on TEZ/IVA. The corresponding LS mean, standard error (SE), 95% CI, and *p*-value will be provided. If the upper bound of the 95% CI is below the pre-defined maximum possible placebo effect, which was specified in the protocol, it will be considered that the study has achieved its primary objective. Summary statistics for change from baseline in $LCI_{2.5}$ through Week 8, and at each visit will also be provided for subjects in the TEZ/IVA treatment group by mutation groups and overall.

For F/F subjects in the placebo treatment group, summary statistics will be provided for change from baseline in LCI_{2.5} through Week 8, and at each visit.

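### Does the within-group LCI2.5 test need a sensitivity analysis for antibiotic-cycle phase and for post-bronchodilator washout tests?

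*Protocol*

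**What the plan says.** SAP section 9.3.1 fits an MMRM to TEZ/IVA subjects only, with visit, mutation group and baseline LCI2.5 as fixed terms. Success means that the upper 95% confidence limit for the average change through Week 8 lies below the threshold. Under SAP section 7.2 that threshold comes from the Study 809-109 placebo group (mean +0.08, SD 1.41): "the one-sided 90% lower bound was -0.10 and is used as an estimate". On which data enter, SAP section 9.3 states: "The analysis will include all available measurements through the last scheduled on-treatment visit, including measurements after treatment discontinuation".

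Two operating rules bear on the measurements:

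- **Antibiotics (protocol 9.5).** For subjects on cycling inhaled antibiotics: "The timing of the first dose of study drug should be synchronized as closely as possible to the first day of inhaled cycling antibiotics". Subjects who alternate two antibiotics have a parallel rule.
- **Bronchodilators (protocol 11.4.1).** Washout testing is meant to be pre-bronchodilator. If a subject forgets to withhold at a later visit, "post-bronchodilator MBW testing will be obtained for that visit only, and the visit will not be rescheduled". If the lapse is on Day 1, "MBW testing should be performed post-bronchodilator and all subsequent MBW testing" should follow suit.

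On data capture, protocol 9.5 says "Information about bronchodilator use during the study will be collected and documented", and protocol 11.4.2 adds "Each spirometry assessment will be recorded in the source documents as pre-bronchodilator or post-bronchodilator". For output, SAP 9.3.1 plans summaries of LCI2.5 change through Week 8, "and at each visit will also be provided for subjects in the TEZ/IVA treatment group by mutation groups and overall", and the same summaries for F/F placebo subjects.

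**The concern.** In a between-arm comparison, a timing or bronchodilator effect common to both arms would cancel on average. Here it passes straight into the least-squares mean that is tested against a constant.

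Suppose the antibiotic cycle is 28 days on and 28 days off (an assumption; the protocol gives no cycle length). The baseline test then falls at the end of an off phase. On the SAP's target days, Day 15 is mid-treatment, Day 29 directly follows the on phase, and only Day 57 returns to the baseline phase. Two of the three averaged visits are therefore out of phase with baseline. If inhaled antibiotics lower LCI, these subjects would appear to improve without any effect of TEZ/IVA.

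The bronchodilator rule looks lopsided in the same way. A pre-bronchodilator baseline may be paired with a post-bronchodilator follow-up, while the reverse pairing is discouraged. The model has no term for either influence, no per-protocol set is defined, and the readable SAP has no sensitivity analysis for them. At stake would be a false claim of efficacy, or a mean change that overstates the drug's effect.

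**Working it through.** **The plan's own figures.** SAP 7.2 gives 40 subjects, 10% dropout, true mean -0.9, SD 1.41 and two-sided alpha 0.05.

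- Evaluable: 40 × 0.9 = 36; SE = 1.41/√36 = 0.235.
- Power = Φ(0.80/0.235 − 1.96) = Φ(1.44) = 92.6% (91.1% with the t distribution). The stated 90% is reproduced.
- Threshold: 0.08 − 1.2816 × 1.41/√n = −0.10 gives n ≈ 101 placebo subjects. The documents do not state this n.

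**Operating point at planned enrolment.** Protocol Table 12-1 has 40 + 12 = 52 subjects on TEZ/IVA.

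- Evaluable: 52 × 0.9 = 46.8; SE = 1.41/√46.8 = 0.206.
- Observed mean needed for success: −0.10 − 1.96 × 0.206 = −0.504.

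**Size of the shifts.** Every effect input here is assumed, and all are taken in the direction that favours the drug.

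- Antibiotic: share of users × effect × 2/3. With 10% to 30% users and an effect of −0.2 to −0.8, the shift is −0.013 to −0.16. At 20% and −0.5 it is −0.067.
- Bronchodilator: share of mismatched tests × effect. With 2% to 10% and −0.2 to −0.8, the shift is −0.004 to −0.08.

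**False success** = Φ((−0.504 − untreated mean − shift)/0.206):

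| Shift | Untreated mean −0.10 | 0 | +0.08 |
|---|---|---|---|
| none | 2.5% | 0.7% | 0.2% |
| −0.067 | 5.1% | 1.7% | 0.6% |
| −0.08 | 5.8% | 2.0% | 0.7% |
| −0.16 | 11.8% | 4.8% | 2.0% |

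The two extremes together (−0.16 − 0.08 = −0.24) give 4.8% at +0.08. With 36 evaluable subjects, a shift of −0.16 gives 10.0% at −0.10 and 2.0% at +0.08.

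**A bound that needs neither n nor SD.** The threshold lies 0.08 − (−0.10) = 0.18 below the documented placebo mean. Any total shift smaller than 0.18 leaves that mean above −0.10, so false success stays below 2.5%.

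**Wider inputs.** A −0.8 effect in 30% of subjects is not a ceiling that the documents supply. With 50% users and an effect of −1.0, the antibiotic shift is 0.5 × 1.0 × 2/3 = 0.33, beyond the 0.18 allowance. A shift of −0.30 at +0.08 gives 8.3% (t-based, 47 evaluable).

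**What excluding subjects would cost.** Dropping 10% to 30% of 46.8 leaves 42.1 to 32.8 subjects and 96% to 90% power at a true −0.9. From the 36 on which the SAP bases its power, dropping 10% or 25% leaves 32 or 27 and t-based power of 87.5% or 81.0%.

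**The case for a change.** The strongest case for acting concerns interpretation more than error rate. A shift in the least-squares mean is the same size whatever the untreated mean is, and no planned analysis separates it from drug effect. The concurrent placebo group is a weak check: 10 subjects give SE = 1.41/√10 = 0.45 and a 95% half-width of about 1.0 (t-based), too wide to resolve shifts of these sizes. The by-visit output is descriptive and is not set against −0.10. A few SAP lines would cost little.

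It stands that the rules exist, that the model ignores them and that the placebo summary is imprecise. The rest is weaker:

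- **Direction is unknown.** The calculation tries only favourable shifts; an opposite shift would make success harder.
- **The bronchodilator rule is not strictly one-sided.** After a post-bronchodilator Day 1, a subject may still arrive without bronchodilator, which gives the reverse mismatch.
- **The threshold may already include these effects.** If Study 809-109 used similar rules, its placebo changes carry them. The documents do not say.
- **The remedies do not isolate the effect.** Removing cycling users changes the population, so a different estimate could reflect different children. Week 8 matches the baseline phase only under the assumed 28/28 cycle, and alternating users follow another pattern.
- **The information is largely there.** With n, mean and SD at each visit, a reader can form an unadjusted Week 8 interval and compare it with −0.10. Protocol 11.4.1 and 11.4.2 use the same withholding times, and the washout precedes spirometry at each visit. The spirometry flag therefore largely serves the washout test too. Part of 11.4.1 is redacted, so a dedicated field cannot be ruled out.

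**Conclusion.** No change to the plan is needed. The absence of a sensitivity analysis is real in the readable text (some SAP efficacy text after 9.3.2 is redacted), but no bias is demonstrated and no stated figure or decision rule is shown to be wrong.

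At the documented placebo mean of +0.08, either shift alone keeps false success at or below about 2.0% across the main assumed ranges. Exceeding 2.5% takes an untreated mean closer to −0.10, both extremes together (4.8% at +0.08), or wider inputs than those ranges. These statements rest on assumed effect sizes, user shares, mismatch rates and cycle length, and on the Study 809-109 placebo mean carrying over to this trial.

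The rules themselves are a fair trade-off. Starting the drug at a fixed point in the cycle standardises the baseline, and keeping a post-bronchodilator test avoids a missing primary measurement. An analyst who wants to set mismatched visits to missing can do so from bronchodilator and spirometry records as an optional supportive run. It would not alter the primary model or its decision rule.

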## 9.6 Administration

On Day 1 through the evening dose administered the day before the Week 8 Visit (last dose of study drug), study drug tablets will be administered orally as shown in Table 9-2.

**Table 9-2 Study Drug Administration**

Genotype	Treatment Arm	Subject Weight on Day 1	Time	Drug(s) and Dose(s) Administered; Route of Administration
F/F	TEZ qd/ IVA q12h	<40 kg	AM	1 × TEZ 50-mg/IVA 75-mg FDC tablet; oral
			PM	1 × IVA 75-mg tablet; oral
		≥40 kg	AM	1 × TEZ 100-mg/IVA 150-mg FDC tablet; oral
			PM	1 × 150-mg tablet; oral
	Placebo	<40 or ≥40 kg	AM	1 × TEZ/IVA-matching placebo FDC tablet; oral
			PM	1 × IVA-matching placebo tablet; oral
F/RF	TEZ qd/ IVA q12h	<40 kg	AM	1 × TEZ 50-mg/IVA 75-mg FDC tablet; oral and 1 × IVA-matching placebo tablet; oral
			PM	1 × IVA 75-mg tablet; oral
		≥40 kg	AM	1 × TEZ 100-mg/IVA 150-mg FDC tablet; oral and 1 × IVA-matching placebo tablet; oral
			PM	1 × IVA 150-mg tablet; oral
	TEZ-matching placebo qd/ IVA q12h	<40 kg	AM	1 × TEZ/IVA-matching placebo FDC tablet; oral and 1 × IVA 75-mg tablet; oral
			PM	1 × IVA 75-mg tablet; oral
		≥40 kg	AM	1 × TEZ/IVA-matching placebo FDC tablet; oral and 1 × IVA 150-mg tablet; oral
			PM	1 × IVA 150-mg tablet; oral

Study drug should be administered within 30 minutes after starting a meal with fat-containing food such as a standard “CF” high-fat, high-calorie meal or snack according to the following guidelines:

1. Study drug should be administered q12h (± 2 hours). For each subject, all doses (morning and evening) of study drugs should be administered at approximately the same time each day. For example, if the morning dose of study drug is administered at 08:00 on Day 1, all subsequent morning doses should be administered between 06:00 and 10:00. On days of scheduled visits, the morning dose of study drug will be administered at the site after predose

assessments have been completed. A meal or snack will be provided by the site for the morning dose of study drug.

2. If a subject's scheduled visit is to occur in the afternoon, the following guidelines must be used for administering either the morning or evening dose:
  - If the dose in the clinic will be within 6 hours of the subject's scheduled morning dose, the subject should withhold their morning dose of study drug, and the morning dose will be administered in the clinic.
  - If the dose in the clinic will be more than 6 hours after the subject's scheduled morning dose, the subject should take the morning dose at home, and the evening dose will be administered in the clinic. In this event, all assessments will be collected relative to the evening dose.
3. For visits after Day 1, subjects will be instructed to bring all used and unused study drug and materials associated with the study drug to the site; study drug will be dispensed at each visit, as appropriate.
4. At the Week 8 Visit, the morning dose of study drug will NOT be administered. The last dose of study drug will be the evening dose administered the day before the Week 8 Visit.

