### 9.3.2.1 Study Drug Treatment Arms

#### F/F Subjects Randomized to TEZ/IVA Treatment

Subjects who are  $< 40$  kg at the Day 1 Visit will receive a morning dose of TEZ 50 mg/IVA 75 mg (fixed-dose combination [FDC] tablet) and an evening dose of IVA 75 mg (tablet).

Subjects who are  $\geq 40$  kg at the Day 1 Visit will receive a morning dose of TEZ 100 mg/IVA 150 mg (FDC tablet) and an evening dose of IVA 150 mg (tablet).

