9.4.8 Other Safety Analysis

9.4.8.1 Serial Lung Function (Post-dose Spirometry)

For the 2-hour and 4-hour post-dose spirometry measurements on Day 1 and Week 2, a summary of raw values and the absolute change from the predose value for ppFEV₁ will be provided at each time point.

The number and percentage of subjects with ppFEV₁ decline ≥ 10 , ≥ 15 , and ≥ 20 percentage points in the absolute change from baseline in predose value will be summarized for scheduled visits.

In addition, the number and percentage of subjects with ≥ 0.10 L or ≥ 0.20 L decrease in the absolute change from baseline through Week 8 for FEV₁ will also be summarized for scheduled visit.

Subjects with ≥ 10 percentage points decrease in absolute change from baseline through Week 8 for ppFEV₁ or ≥ 0.10 L decrease in the absolute change from baseline through Week 8 for FEV₁ will be listed.

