 - Assessments at safety follow-up (SFU) visit will follow the windowing rules for regular visits if they fall within the upper boundary of the window for Week 8, or remain as SFU if they go beyond the upper boundary of the window for Week 8.
5. If there is more than one measurement available within the same visit window for safety parameters, then
 - The record closest to the target day will be used.
 - If there are multiple records within the same distance from the target day, the latest record will be used; or
 - SFU visit will not be windowed; instead, it will be used according to the nominal visit in relevant analyses.
6. Spirometry assessments, BMI, weight, and height will be used for [REDACTED] safety purpose. Their measurements will follow the visit windowing rules for efficacy parameters.
7. For post-dose spirometry, Day 1 and Week 2 will be nominal.

Special handling for ECG:

- On Day 1, the pre-dose measurements will be collected as triplets; the average of the triplicate will be used as pre-dose measurement on Day 1. Only pre-dose measurement with nominal visit names related to the triplets shall be used in this average.
- For other post-dose visits, the visit window in the above table will apply.

▪ **Appendix B: Standards for Safety and Efficacy Variable Display in TFLs**

Continuous Variables

The precision for continuous variables has been specified in the Vertex Standard Programming Rules document (Version 1.0, December 2015):

Categorical Variables: Percentages will be presented to 1 decimal place.

▪ **Appendix D: Imputation Rules for Missing Prior/Concomitant Medication Dates**

Imputation rules for missing or partial medication start/stop dates are defined below:

1. Missing or partial medication start date:
 - a. If only DAY is missing, use the first day of the month.
 - b. If DAY and Month are both missing, use the first day of the year.
 - c. If DAY, Month and Year are all missing, use a date before the first dose date (in practical, use January 01, 2000 to impute).
2. Missing or partial medication stop date:
 - a. If only DAY is missing, use the last day of the month.
 - b. If DAY and Month are both missing, use the last day of the year.
 - c. If DAY, Month and year are all missing, assign ‘continuing’ status to stop date (in practical, use December 31, 2050 to impute).

In summary, the prior, concomitant or post categorization of a medication is described below.

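### Week 2 serial spirometry timed from a clinic evening dose (IVA only) is not separated from readings taken 2 and 4 hours after the TEZ/IVA tablet

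*Protocol*

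**What the plan says.** Table 9-2 and Protocol 9.3.2.1 place tezacaftor only in the morning fixed-dose tablet. In both TEZ/IVA arms the evening dose is a single ivacaftor tablet. One evening row of Table 9-2 omits the drug name, but 9.3.2.1 identifies it as ivacaftor.

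Guideline 2 below Table 9-2 splits afternoon visits in two, by the gap between the scheduled morning time and the clinic dose:

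- When the gap is within 6 hours, "the subject should withhold their morning dose of study drug, and the morning dose will be administered in the clinic".
- When the gap exceeds 6 hours, "the subject should take the morning dose at home, and the evening dose will be administered in the clinic". For such a visit the protocol adds that "all assessments will be collected relative to the evening dose".

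Table 3-1 (spirometry footnote) asks for extra spirometry 2 and 4 hours postdose, each ± 30 minutes, on Day 1 and at Week 2. It does not say which dose is meant.

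For those readings SAP 9.4.8.1 plans "a summary of raw values and the absolute change from the predose value for ppFEV₁ will be provided at each time point". SAP 9.4 presents safety endpoints by treatment group and overall. Appendix A Note 7 adds: "For post-dose spirometry, Day 1 and Week 2 will be nominal". Neither document flags, separates or excludes serial readings timed from an evening dose.

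**The concern.** Serial lung function is a named component of the secondary safety endpoint (Protocol 7.2, SAP 6.2). A reader of the Week 2 table for the TEZ/IVA group will take its 2- and 4-hour columns to mean 2 and 4 hours after the combination tablet, as they do on Day 1. On the more-than-6-hour branch they mean 2 and 4 hours after ivacaftor alone, compared with a reference value measured hours after that morning's combination tablet. An early change after the combination tablet could come and go before the reference is taken.

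Two further features make the mixing awkward. Day 1 and Week 2 are no longer like for like. And among F/RF children on this branch, the clinic tablet in the TEZ/IVA arm is the same ivacaftor tablet given in the ivacaftor monotherapy arm, so the arms do not differ in the dose that the readings follow.

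The SAP already recognises that the two daily doses are different agents: SAP 9.4.1.1 records the action taken after an adverse event separately for the morning and the evening dose. Serial spirometry has no such distinction.

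**Working it through.** The plan states no figure for this point, so the check is one of timing, followed by what can and cannot be said about size.

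**1. Hours since the fixed-dose tablet, more-than-6-hour branch.** Take the home dose at its scheduled time as hour 0. The clinic dose is at hour c, with c > 6. A reading t hours postdose falls at c + t, ± 0.5.

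| Reading | Nominal | Earliest in window |
|---|---|---|
| Predose reference | taken before the clinic dose; more than 6 h if taken just before it | – |
| 2-hour | > 6 + 2 = 8 h | > 8 − 0.5 = 7.5 h |
| 4-hour | > 6 + 4 = 10 h | > 10 − 0.5 = 9.5 h |

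The 6 hours run from the scheduled time. Guideline 1 lets a morning dose be up to 2 hours late. That would shorten each interval by up to 2 hours, so the earliest window limits become 5.5 and 7.5 hours. These still lie beyond the intended upper limits of 2.5 and 4.5 hours.

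**2. The same, if the 12-hourly interval (± 2 h) is also kept.** Then c runs from 10 to 14. The 2-hour reading falls at 12 to 16 h and the 4-hour reading at 14 to 18 h after the fixed-dose tablet.

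**3. Afternoon visits dosed within 6 hours.** The morning tablet is given in clinic, so the readings are 2 and 4 h after it, as intended. With the protocol's 08:00 example, this covers any clinic dose up to 14:00.

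**4. Day 1.** The first dose of study drug is given on Day 1 (Protocol 9.1.2), so no home dose precedes it and the branch cannot apply.

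**5. How often could the branch arise?** With an 08:00 morning dose and the 12-hourly window, the evening dose is at 18:00 to 22:00 and the 4-hour test at 22:00 to 02:00. Going by the 6-hour rule alone, the clinic dose is after 14:00 and the 4-hour test after 18:00. Either is a long visit for a child aged 6 to 11.

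**6. Effect on the Week 2 mean.** Let s be the share of TEZ/IVA children on the branch, a the mean change at 2 (or 4) hours after the fixed-dose tablet, and b the mean change recorded on the branch.

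Pooled mean = (1 − s)a + sb, so the shift from a is s(b − a).

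The documents give none of s, a or b. From Table 12-1, the planned TEZ/IVA group is 40 + 12 = 52, so each affected child contributes 1/52 = 1.9% of the mean. If s = 0, nothing changes. The sign of b − a is unknown: b could be near zero, or values could be recovering from an earlier fall during the 4 hours.

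**The case against.** The strongest reply is that the branch will hardly ever be used at this visit. Guideline 1 has the morning dose given at the site on visit days, and step 5 shows how late the 4-hour test would run. Safety is descriptive only, the Day 1 serial spirometry is intact, and SAP 9.4.1.4 separately summarises respiratory events such as bronchospasm, wheezing and dyspnoea. The evening tablet is also study drug, and the protocol deliberately times assessments to it. All of this stands, and it limits the weight of the point. It does not remove the gap: guideline 2 is mandatory where it applies, and the SAP has no rule for the records it produces.

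A reader might infer more than the documents support:

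- *That every afternoon Week 2 visit is affected.* It is not; within 6 hours the morning tablet is given in clinic.
- *That the affected readings do not follow TEZ/IVA at all.* The child took the combination tablet that morning. The defect is that the readings are not 2 or 4 hours after it.
- *That the Week 2 result is diluted towards no change, or that a safety signal is hidden.* That needs a known share of visits and no acute change after ivacaftor. Neither is documented.
- *That counts of children with a marked fall would shrink.* The ppFEV₁ decline counts in SAP 9.4.8.1 (10, 15 and 20 points) use predose values, so the 2- and 4-hour readings do not enter them.

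Pooling is itself an inference, from nominal visit assignment and the absence of any separating rule; no sentence states it outright.

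**Conclusion.** The point holds in a narrow form and is minor. If the rules are followed as written, a Week 2 visit on the more-than-6-hour branch yields readings labelled 2 and 4 hours that are more than 8 and 10 hours after the combination tablet (7.5 and 9.5 with the window). They are compared with a reference already more than 6 hours after it, and they enter the same summary as correctly timed readings. These figures assume that the home dose was taken at its scheduled time and that the reference is measured just before the clinic dose.

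The mislabelled timing follows from the text alone. The number of children affected does not; it may be near zero, and no direction or size of distortion can be claimed. The primary endpoint summary is not the subject of this point.

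The timing rules also do not fit together. The branch opens at 6 hours, whereas the 12-hourly window implies at least 10 hours between doses, so a clinic evening dose between 6 and 10 hours satisfies one rule and breaches the other.

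**What to change.** In SAP 9.4.8.1 and Appendix A Note 7, for all arms:

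1. Base the Week 2 summary of 2- and 4-hour change from predose on subjects whose in-clinic dose was the morning dose.
2. Summarise or list separately the records where the in-clinic dose was the evening dose.
3. Report both counts.

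A flag in the existing table and listing would be a lighter alternative, but the split makes the main columns mean what their labels say. The cost is a sentence in each place, a filter on the dose given in clinic, and a slightly smaller n at Week 2. If no evening-dose records occur, the figures do not change.

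Separately, the sponsor should reconcile the more-than-6-hour branch of guideline 2 with the 12-hourly ± 2-hour window, and state which dose the postdose spirometry in Table 3-1 refers to. No dosing rule is proposed here.
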